Design and rationale of the Prevention of radial Artery occlusion after Transradial accEss using
NitroglyceriN (PATENS)

NCT03158532

Florianópolis, dec/04/2024

Design and rationale of the Prevention of radial Artery occlusion after Transradial accEss using NitroglyceriN (PATENS)

Abstract

Background

Radial artery occlusion (RAO) is an important access site complications after transradial catheterization (TRC). Acute loss of radial artery patency after TRC is thought be due to a thrombotic process, and a bigger sheath-to-radial-artery ratio could reduce the incidence of RAO. Nitroglycerin acts through the liberation of nitric oxide (NO), which promotes muscle relaxation and vasodilation. Leading to a bigger sheath-to-radial-artery ratio the nitroglycerin administration could help to keep the radial artery patency. The aim is to study if nitroglycerin is superior to placebo concerning incidence of radial artery occlusion, confirmed by vascular Doppler ultrasound, up to 24 hours after catheterization.

Methods/Design

PATENS is a national, multicenter, superiority, 2-by-2 factorial, randomized clinical trial. Two thousand one hundred twenty-eight patients submitted to TRC will be randomized to either nitroglycerin or placebo, administered intra-arterially through the sheath, in two different moments during TRC: after the arterial sheath insertion, at the beginning of procedure, and at the end of the radial procedure, before sheath removal.

Results

The primary efficacy objective is to test the hypothesis that nitroglycerin, dose of 500 mcg, is superior to placebo in decreasing rates of radial artery occlusion on ultrasound Doppler analysis up

to 24 hours after procedures. As secondary objectives, the trial will evaluate the incidence of radial artery occlusion 30 days after catheterization. Enrollment was initiated in August 2017, and the inclusion phase is expected to last until the second half of 2019.

Conclusions

The PATENS trial will help define the role of prophylactic nitroglycerin as a RAO avoidance strategy in patients with submitted to TRC.

Trial registration

ClinicalTrials.gov identifier: NCT03158532

Background

The use of the transradial approach (TRA) for coronary catheterization has increased over the years, worldwide. Radial artery is nowadays utilized by default for percutaneous coronary procedures in many centers, thanks to the reduced rates of vascular and bleeding complications and easier post-procedural management. The use of TRA also improves patient comfort, saves costs and it has an equivalent procedural success when compared to the femoral approach.

Although it is widely accepted by cardiologists and patients, some problems still exist. One of the major limitations is the development of radial artery spasm (RAS), which can reduce success rates, leading to femoral conversion, and cause significant pain to patients. The incidence of RAS varies between 2% and 34%. Aiming prevent RAS, the use of prophylactic intraarterial vasodilators is

routinely recommended by experts, mainly verapamil or nitroglycerin. Most catheterization laboratories habitually use some medication to prevent RAS, however, it is not a consensus.

Another important complication, often underestimated, is the post-procedural radial occlusion (RAO). Incidence of radial pulse loss has been reported to range from 1% to 12%. The benign nature of such an event has been constantly emphasized due to the dual blood supply to hand from the palmar arch. Mostly, the occurrence of radial occlusion is asymptomatic, symptomatic radial occlusion requiring medical attention occurred in only 0.2% of patients, but hand ischemia caused by RAO has been described. The most important aspect is that once artery is occluded, it can not be used neither as access site for future catheterization, nor be used as a conduit for bypass surgery nor fistula formation in hemodialysis patients. The use of small caliber catheters, adequate dose of heparin administration, immediate sheath removal after procedure, patent hemostasis technique and short time of compressive bandage are the key elements to reduce the risk of artery occlusion. Notably the presence of radial pulse does not exclude radial occlusion due to presence of collateral circulation; it can be more accurately evaluated by absence of antegrade flow in vascular doppler ultrasound. In fact, many operators do not assess radial artery patency before discharge.

Acute loss of radial artery patency after cardiac catheterization is thought to be due to a thrombotic process. Sheath insertion leads to local endothelial injury and cessation of blood flow in the radial artery, creating an environment conducive to thrombosis. RAO tends to occur early after transradial catheterization, and roughly 50% of patients have spontaneous recanalization of the artery within 1 month. Direct support for the thrombotic hypothesis has come from recent studies that have confirmed the presence of radial artery thrombus on vascular ultrasound, angiography, and pathology. Transradial catheterization can negatively affect radial artery structure as well. A study using optical coherence tomography found that 67% of radial arteries had intimal tears and 36% had medial dissections immediately after transradial PCI. A study of radial artery function after transradial catheterization found that flow-mediated dilatation was blunted up to 9 weeks. The

radial artery response to nitroglycerin was also decreased, suggesting that the impairment in function was more than just temporary damage to the endothelium and involved long-term changes to the smooth muscle layer.

Nitrates in intra-arterial have been widely studied in prevention of spasm. Nitroglycerin binds to the surface of endothelial cells and undergoes two chemical reductions to form nitric oxide (NO). The nitric oxide then moves out of the endothelial cell and into an adjacent smooth muscle cell, where it promotes the formation of cyclic guanosine monophosphate (cGMP), which promotes muscle relaxation. A bigger sheath-to-radial-artery ratio could reduce the incidence of RAO, indeed current data show that nitroglycerin intra-arterial at the end of the procedure reduce the incidence of radial artery occlusion, so the main objective of this study is to evaluate whether administration of nitroglycerin at the start of a transradial procedure may preserve the patency of the radial artery; as well, confirm if nitroglycerin administration just before sheath removal helps to keep the radial artery patency, probably mediated by vasodilation.

Methods

This is a randomized, multicenter, double-blind, placebo-controlled phase III study (Clinicaltrials.gov identifier NCT 03158532) with an all-comers design, comparing the use of nitroglycerin to decrease the rate of radial artery occlusion after transradial catheterization. Using a 2-by-2 factorial design, we will randomly assign 2128 patients with a clinical indication for coronary angiography (ad hoc angioplasty allowed) or percutaneous coronary intervention (PCI) to receive either 500 micrograms of nitroglycerin or placebo (0,9% sodium chloride), administered intra-arterially through the sheath, in two different moments during transradial catheterization: shortly after the arterial sheath insertion and at the end of the radial procedure, before sheath removal. Written, informed consent will be obtained from each subject. The study protocol has been presented to the institutional medical ethical committee of all participating hospitals to comply with local standards.

Randomization and final acceptance into the study will take place after successful radial artery cannulation and guide wire advanced into the radial arterial lumen through the needle to allow exclusion of failed radial puncture.

Patient population

All eligible patients are aged 18 years or over with a clinical indication for coronary angiography (ad hoc angioplasty was allowed) or percutaneous coronary intervention (PCI) if the following pre-requisites are met: (i) choice of the operator to use the transradial access route and (ii) use of sheath size 5 or 6 French. Allen test was not obligatory performed. The exclusion criteria were: (I) primary angioplasty due to acute myocardial infarction; (ii) intubated patients; (iii) complications during procedure (cardiac arrest, pulmonary oedema, cardiogenic shock, and stroke); (iv) prior inclusion in this trial; (v) known allergy or intolerance to nitrates; (vi) patients medicated with continuous intravenous nitrates or whom received any nitrates on the last hour and (vii) use within 24 hours prior to randomization of phosphodiesterase inhibitors.

Outcomes

Primary outcome

RAO: incidence of radial artery occlusion as confirmed by the absence of antegrade flow in vascular high resolution duplex ultrasound, up to 24 hours after catheterization.

Secondary outcomes

Late RAO: incidence of radial artery occlusion as confirmed by the absence of antegrade flow in vascular high resolution duplex ultrasound, 30 days after catheterization.

Comfort assessment: pain felt by the patient in the forearm, assessed using numeric pain rating scale. The 11-point numeric scale ranges from '0' representing one pain extreme (e.g. "no pain") to

'10' representing the other pain extreme (e.g. "worst pain imaginable"). Only the numbers themselves are valuable answers, meaning that there are only 11 possible answers in the 0–10 interval.

Spasm (operator evaluation): catheter friction, as experienced by the operator (subjective measure), on a predetermined score: 0. No resistance during catheter manipulation or pain reported by the patient; 1. No resistance during catheter manipulation, but with pain reported; 2. Light resistance during catheter manipulation; 3. Moderate to strong resistance during catheter manipulation; 4. Catheter trapping.

Procedure duration: total duration of the procedure, from sheath insertion to last catheter removal.

Radiation exposure: total radiation used in the procedure (mGy).

Study definitions

RAO: the absence of an antegrade flow in radial artery was recorded by doppler ultrasound study.

RAS: will be defined as spasm when: operator evaluation of spasm bigger than 2 by predefined scale; need of spasmolytic medication; access site conversion due to confirmed angiographic evidence of spasm.

Access site conversion: impossibility of complete procedure without another arterial site access. It may be due to spasm or anatomical reason, and should be confirmed with angiography.

Radial puncture attempt: defined as any skin puncture with positive blood draw through the needle.

Local hematoma: will be classified according to the EASY scale: I, ≤ 5 cm diameter; II, ≤ 10 cm diameter; III, > 10 cm but not above the elbow; IV, extending above the elbow; and V, anywhere with ischemic threat of the hand.

Major bleeding: will be graded according to the Bleeding Academic Research Consortium definition: Type 3 ((3a) bleeding with hemoglobin drop ≥ 3 and < 5 g/dL, or packed red cells transfusion; (3b)

bleeding with hemoglobin drop ≥ 5 g/dL, heart tamponade, bleeding requiring surgical intervention or bleeding requiring intravenous inotropic drugs; (3c) intracranial hemorrhage; subcategories confirmed by autopsy, imaging examinations or lumbar puncture; intraocular bleeding with vision impairment) or type 5 bleeding ((5a) possibly fatal bleeding, (5b) definitive fatal bleeding).

Transradial procedure

Local anesthesia will be administered with a subcutaneous injection of 1% lidocaine after skin preparation. Radial artery access will be obtained using either anterior or counter-puncture technique based on the operator's preference, using a 21-gauge bare needle or 20/22 G sheath covered needle, following which a 5Fr or 6Fr hydrophilic sheath will be inserted over a guidewire. Then, the patient will receive the randomized solution (500 micrograms nitroglycerin or placebo), plus heparin 5,000 units through the radial sheath as an intra-arterial bolus. Additional heparin will be given in cases of PCI (total 100 UI/kg). Doses of heparin are used according to our study protocol. The use of additional medication, either vasodilators or analgesics, is left to operators' discretion.

No routine

intravenous sedation was given. Transradial coronary angiography and/or PCI will be performed according to standard techniques, by the choice of operators. At the end of procedure, and before sheath removal, four to five ml of blood will be aspirated through the sheath to remove any residual thrombus and in a blinded fashion, either a 500 micrograms nitroglycerin or placebo will be administered through the radial sheath. Then, the arterial sheath will be removed and hemostasis will be achieved.

Arterial hemostasis

A compression device designed to assist hemostasis of the radial artery after a transradial procedure will be applied according to a previously validated protocol. Immediately after procedure

completion, the sheath is initially pulled by approximately 2 to 3 cm. The device is applied to the patient with the green marker (located in the center of the larger balloon) positioned exactly at the puncture hole to aid in the location, visualization and control of possible bleeding. The balloon is inflated with an adequate syringe injecting 15 ml of air with simultaneous and total sheath removal, resulting in the absence of active bleeding. If bleeding occurs, additional 3 ml of air is injected to obtain complete hemostasis. The device is then slowly deflated to the lowest allowable volume (minimum 7 ml) while maintaining hemostasis. If bleeding occurred, 1 ml of air was reintroduced from the bleeding point. Radial artery patency was evaluated utilizing plethysmographic and pulse oximetry evaluation, with sensor placed over the thumb or index finger, and occlusion (manual pressure) of the ulnar artery. Absence of plethysmographic waveform is indicative of interruption of radial artery flow. After 1 hour post diagnostic procedure or 2 hours post intervention, 3 ml of air is removed every 15 minutes. If bleeding occurs during any stage of device removal, the volume of air needed for hemostasis is again injected, restarting the deflation process 60 minutes later. When all the air is removed, and there is no bleeding, the device is removed and the access site is covered with a simple dressing. Dressing should not encircle the entire wrist.

Statistical analysis

The primary analysis of the study is a superiority comparison between the use of nitroglycerin to decrease RAO, in all randomized patients, based on the intention-to-treat principle.

Using our primary end point to estimate the sample size, we suppose to have a 30% reduction in RAO for each trial intervention, considering potential interaction between them. Estimating RAO prespecified in the primary outcome of approximately 11.7% without use of nitroglycerin, with an alpha level of 0.05 and a beta level of 0.20, the minimum estimated sample size per group was established as 1064 individuals. As we do not expect any subsequent loss of follow-up due to the short primary evaluation, the enrollment of 2128 patients would provide sufficient power to the

study. Continuous variables will be described as means and standard deviation and compared using Student's t -test for normally distributed variables or assessed using Mann-Whitney test when not normally distributed. Categorical variables are expressed as frequencies and group percentage and will be compared with the chi-square or Fisher's exact tests. To test the interaction between interventions, we used a multivariable logistic-regression model that included the two randomized treatments and their interaction as parameters. In the analysis of the primary and secondary end points, a two-tailed p value of less than 0.05 will be considered statistically significant. No prespecified interim analysis will be performed. All analyses will be performed using SPSS version 22 (SPSS Inc., Chicago, Illinois).

Discussion

Cardiac catheterization is a common procedure and is need in many clinical scenarios and many times repeated procedures are need. The use of TRA is increasing aiming to improve patient comfort, save costs and reduce rates complications. This implies that the occurrence of RAO should be considered because, once it's occurred, it is impossible to use radial access for future catheterization. In most cases RAO occurs promptly after the procedure and up to 50% of patients have spontaneous recanalization of the artery within 1 month. A palpable pulse does not exclude the diagnosis of RAO: collateral blood flow may supply the periphery of the radial artery distally to the occlusion, giving a false impression of radial artery patency. Therefore, RAO can often be undiagnosed. Radial artery patency is better evaluated with clinical testing as the reverse Barbeau's test and with Doppler ultrasonography. Many interventions are suggested to reduce the risk of RAO, mainly anticoagulation, patent hemostasis and a bigger sheath-to-radial-artery ratio. Although nitroglycerin promotes vasodilation and thus improves the sheath-to-radial-artery ratio, no recommendation is done to its routinely use. Handling confounding factors such as anticoagulation and hemostasis, this test has an ideal design to address the question of whether routine use of the

nitroglycerin approach is superior to not use with respect to the occlusion occurrence, including possible predictors.

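### Exclusion criterion (iii), complications during the procedure, has no time limit; as written it acts on randomised patients and conflicts with the all-randomised primary analysis

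*Combined protocol and SAP*

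**What the plan says.** All references are to the combined protocol and SAP.

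- **Patient population.** Exclusion criterion (iii) reads "complications during procedure (cardiac arrest, pulmonary oedema, cardiogenic shock, and stroke"). It names no reference time. Criterion (vii), in the same list, is explicitly tied to randomisation.
- **Methods.** "Randomization and final acceptance into the study will take place after successful radial artery cannulation and guide wire advanced into the radial arterial lumen". The reason given for this timing is to screen out failed punctures; procedural complications are not mentioned.
- **Transradial procedure.** The sequence starts with "Local anesthesia will be administered with a subcutaneous injection of 1% lidocaine after skin preparation". Arterial access comes next, "following which a 5Fr or 6Fr hydrophilic sheath will be inserted over a guidewire". Only once the sheath is in place is the first study dose given: "Then, the patient will receive the randomized solution (500 micrograms nitroglycerin or placebo), plus heparin 5,000 units through the radial sheath". After that, "Transradial coronary angiography and/or PCI will be performed according to standard techniques". The second study dose is given "At the end of procedure, and before sheath removal".
- **Secondary outcomes.** For the duration outcome, the procedure is timed from insertion of the sheath until the last catheter is out.
- **Statistical analysis.** The primary comparison is made "in all randomized patients, based on the intention-to-treat principle".

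No section defines a modified intention-to-treat set. None says whether a randomised patient who meets (iii) stays in the analysis.

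**The concern.** An exclusion criterion should be decidable at the moment of randomisation. This one mostly cannot be, because the events it names arise in a period that begins at about that moment and includes the first study dose. A site or analyst who follows the list literally would drop a randomised patient because of something that happened after assignment. One who follows the Statistical analysis section would keep that patient.

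If patients are dropped, the groups compared are no longer the groups as randomised. The exposure is mainly in the start-of-procedure comparison, which the Background presents as the main objective. The first dose precedes most of the procedure and could in principle affect these events. The second dose comes at the end and cannot affect events before it.

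Bias needs two things together: removals that differ between arms in number or in type of patient, and an RAO risk among those removed that differs from average. Removal would also take cardiac arrest, pulmonary oedema, shock and stroke out of any comparison by arm.

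**Working it through.** **Step 1: order of events.**

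| Event | Relative to randomisation | Could (iii) apply? |
|---|---|---|
| Local anaesthesia, puncture | Before | Yes, as an ordinary pre-randomisation exclusion |
| Wire in radial lumen | Randomisation point | – |
| Sheath insertion, first dose | After | Yes, on a randomised patient |
| Angiography and/or PCI | After | Yes, on a randomised patient |
| Second dose, sheath removal | After | Yes, on a randomised patient |

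The duration outcome gives the documents' only operational boundary for the procedure, and it lies wholly after randomisation. It was written for an outcome, so it supports the literal reading but does not prove it. For a post-randomisation event, (iii) and the all-randomised analysis cannot both be followed.

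**Step 2: inputs for the size.**
- From Statistical analysis: RAO of 11.7% without nitroglycerin, 1064 per group, two-sided 5% level.
- Assumed, because the documents give no figures: the fraction removed in each arm (`e`) and the RAO risk among those removed (`pf`). No true drug effect on RAO.

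The plan has no figure of its own on this point. The 1064 is taken as given. The usual two-proportion formula for 11.7% versus 8.19% gives 1140 per group, and 1064 gives 77.2% power; that is a separate matter and nothing below depends on it.

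**Step 3: formulas.**
- RAO after removal: `p' = (0.117 − e·pf) / (1 − e)`, with `1064·(1 − e)` patients left in the arm.
- Type I error of the pooled two-sided z-test: `Φ((−1.96·s0 − d)/s1) + 1 − Φ((1.96·s0 − d)/s1)`. Here `d` is the difference in `p'`, and `s0` and `s1` are its pooled and unpooled standard errors.

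**Step 4: one case in full** (`pf` = 50%, 1% removed on placebo, 2% on nitroglycerin).
- Placebo: (0.117 − 0.005)/0.99 = 0.1131.
- Nitroglycerin: (0.117 − 0.010)/0.98 = 0.1092.
- Relative risk: 0.965.
- d = −0.00395 and s0 ≈ s1 ≈ 0.01373, so d/s1 = −0.288.
- Type I error: Φ(−1.672) + Φ(−2.247) = 0.0472 + 0.0123 = 0.0595.

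**Step 5: range, start-of-procedure comparison.**

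| RAO in those removed | Removed, placebo vs nitroglycerin | Patients (about) | Relative risk | Type I error |
|---|---|---|---|---|
| 50% | 0.1% vs 0.2% | 1 vs 2 | 0.997 | 5.0% |
| 50% | 0.5% vs 1% | 5 vs 11 | 0.983 | 5.2% |
| 50% | 1% vs 2% | 11 vs 21 | 0.965 | 5.95% |
| 50% | 1% vs 3% | 11 vs 32 | 0.930 | 9.0% |
| 25% | 0.5% vs 1% | 5 vs 11 | 0.994 | 5.0% |
| 25% | 1% vs 2% | 11 vs 21 | 0.988 | 5.1% |
| 25% | 1% vs 3% | 11 vs 32 | 0.976 | 5.5% |
| 11.7%, or equal removal of similar patients | any | – | 1.000 | 5.0% |

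With the excess on placebo instead, the last three 50% rows become relative risks of 1.017, 1.036 and 1.076, with the same type I error.

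Removals needed for a type I error of 6%:
- 2:1 imbalance: about 22 vs 11 patients at 50% RAO, or 60 vs 30 at 25%.
- 3:1 imbalance: about 17 vs 6 at 50% RAO, or 47 vs 16 at 25%.

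**Step 6: end-of-procedure comparison.** In a factorial simulation (four cells of 532, 400,000 replicates, removal depending on the first dose only), the start comparison gave 5.0%, 5.2%, 5.9% and 9.0% for the four 50% rows. The end comparison stayed at 5.0% throughout.

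**Step 7: power** for 11.7% versus 8.19%: 77.2% with nobody removed, 77.0% with 0.5% removed per arm, 76.8% with 1% removed per arm.

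**The case against.** The strongest reply is that there is no real conflict. Eligibility criteria govern entry, the protocol couples final acceptance with randomisation, and the analysis set is stated separately and plainly as everyone randomised. On that reading (iii) is only loosely worded. The reading is possible, and the sponsor may intend it. But it leaves (iii) with nothing except the anaesthesia and puncture interval. The text sets no such limit, and the duration outcome treats the procedure as starting later. The Statistical analysis section does not mention the criterion, so a patient recorded as excluded could be treated as never properly enrolled.

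The second reply is size, and it largely stands. The 9.0% case needs 3% of one arm to have such an event, a threefold imbalance, and an RAO risk more than four times 11.7% (50/11.7 = 4.3). The documents support none of these. Blinding stops anyone choosing removals by known arm, though it does not stop a true drug effect on the events. Excluding primary angioplasty for infarction and intubated patients plausibly makes the events rarer, but no rate is given.

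Third, restoring removed patients helps fully only if they have a 24-hour Doppler result, and some may not. That is a real limit on the remedy.

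**Conclusion.** The concern holds. As written, (iii) acts mostly on events after randomisation and cannot be applied together with an analysis of all randomised patients, and no section settles which prevails. The documents do not show that anyone was actually removed.

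The size is unknown. On the assumptions above, the effect is nil to small unless removals are numerous, unequal between arms and concentrated in patients at high RAO risk. It falls on the start-of-procedure comparison; the end-of-procedure comparison is unaffected if removal depends only on the first dose. The loss of power is about 0.4 percentage points with 1% removed per arm.

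The case for acting therefore rests on an unresolved primary analysis set, not on a demonstrated large bias. It should be fixed.

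**What to change.** Reconcile the Patient population and Statistical analysis sections:

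1. Limit criterion (iii) to events before randomisation.
2. State that patients who have these complications after randomisation stay in their assigned group in the primary analysis.
3. If enrolment has closed, restore any randomised patients removed under (iii), and report their number and the complications by arm.

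Whether such patients receive the second study dose is a clinical matter for the sponsor and is not addressed here. General handling of missing Doppler results is a separate point.

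The cost is one line in the eligibility criteria and one in the statistical section, with no change to sample size or procedures. The Abstract expected inclusion to run until the second half of 2019 and the document is dated December 2024, so enrolment may have closed, although the documents do not say. If it has, the first item cannot change who was enrolled, and the useful parts are the analysis-set sentence and the count by arm. The downside is that a few of these patients may have no 24-hour Doppler result.

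### The plan has no rule for missed 30-day scans, and the tests it names for late RAO would by default drop those patients and ignore their 24-hour Doppler

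*Combined protocol and SAP*

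**What the plan says.** Under Outcomes, both ultrasound endpoints are binary and rest on the same finding. The primary is read on "vascular high resolution duplex ultrasound, up to 24 hours after catheterization"; the late one is "Late RAO: incidence of radial artery occlusion as confirmed by the absence of antegrade flow" on "vascular high resolution duplex ultrasound, 30 days after catheterization".

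Under Statistical analysis:

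- The analysis set is "in all randomized patients, based on the intention-to-treat principle". This is said of the primary analysis; no set is named for 30 days.
- Attrition is dismissed in one clause: "As we do not expect any subsequent loss of follow-up due to the short primary evaluation".
- On tests: "Categorical variables are expressed as frequencies and group percentage and will be compared with the chi-square" or Fisher's exact tests. The one regression described is a "multivariable logistic-regression model that included the two randomized treatments and their interaction as parameters", given as the interaction test.
- Secondary endpoints are tested at a two-tailed 0.05 level, like the primary.

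On how the two scans relate, the Background says: "RAO tends to occur early after transradial catheterization, and roughly 50% of patients have spontaneous recanalization of the artery within 1 month". The Discussion repeats this as up to 50%.

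Nothing says how a missed 30-day scan is handled, or that the 24-hour result will be used in the late comparison.

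**The concern.** The reason given for expecting no loss is the short primary window. It cannot cover a scan a month later, for which the patient generally has to come back. Once some scans are missing, a chi-square or Fisher test, or a logistic model with treatment terms only, uses only the patients who have an outcome. That is what would happen by default under the plan as written.

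Two different things could then go wrong. If returning is linked to the 24-hour finding, the returners have a different mix of occluded and patent arteries from the randomised patients, so the reported late rates and absolute difference are off. If loss is unrelated to anything, the rates are sound but precision falls, although part of it could be recovered from a 24-hour scan planned for everyone.

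The late rate matters because the Background gives loss of the artery for later access, bypass conduit or fistula as the main harm of RAO. With about half of occlusions reopening, the 30-day absolute rate shows how much of that harm persists.

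**Working it through.** **Inputs from the documents.** 24-hour RAO 11.7% without nitroglycerin; 30% relative reduction; 1064 per group; two-sided alpha 0.05; about 50% of occlusions reopen within a month.

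**Assumed.** No new occlusion after 24 hours (0% to 1% in the range check) and all return rates, because the documents give neither.

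**The plan's own figure.** No sample size or power is stated for 30 days. The 1064 is for the primary endpoint and does not reproduce: 11.7% v 0.7 × 11.7% = 8.19% needs 1140 per group for 80% power, and 1064 gives 77.2%. That is a separate matter; 1064 is used below as stated.

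**Step 1. Expected late rates.** 0.117 × 0.5 = 5.85% and 0.0819 × 0.5 = 4.095%. The difference is 1.755 points (1.76) and the risk ratio 0.700.

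**Step 2. How much the 24-hour scan tells us.** With p the 24-hour rate, the late outcome has variance (p/2)(1 − p/2), of which p(1 − p) × 0.25 is explained by 24-hour status.

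- Control: 0.02583 / 0.05508 = 47%.
- Nitroglycerin: 0.01880 / 0.03927 = 48%.
- With 40–60% reopening and 0–1% new occlusion, the share runs from about 29% to 58%.

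A patent artery is nearly settled at 24 hours. An occluded one is an even bet.

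**Step 3. Return linked to 24-hour status.** Let r1 and r0 be the return probabilities for occluded and patent patients. The rate seen among returners is 0.5·p·r1 / [p·r1 + (1 − p)·r0]. For r1 = 0.95 and r0 = 0.80, control is 0.055575 / 0.81755 = 6.80% and nitroglycerin 0.038903 / 0.812285 = 4.79%.

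| Return, occluded / patent (assumed) | Late RAO, control v nitroglycerin | Difference (points) | Relative to 1.755 | Risk ratio |
|---|---|---|---|---|
| 100% / 100% | 5.85% v 4.10% | 1.76 | – | 0.700 |
| 95% / 80% | 6.80% v 4.79% | 2.01 | 14% too large | 0.705 |
| 98% / 70% | 7.82% v 5.55% | 2.27 | 29% too large | 0.710 |
| 60% / 90% | 4.06% v 2.81% | 1.25 | 29% too small | 0.692 |

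Under the null, p and the reopening rate are equal in both arms. If return depends only on 24-hour status, the formula then gives the same value in each arm, so no false difference is created.

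**Step 4. What standardisation does.** Estimate the late rate in an arm as q·a + (1 − q)·b. Here q is the 24-hour occlusion proportion in everyone randomised to that arm, and a and b are the 30-day occlusion proportions among returners who were occluded and patent at 24 hours. In all rows above a = 0.5 and b = 0, so control is 0.117 × 0.5 = 5.85%, nitroglycerin is 4.10%, and the true difference returns.

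**Step 5. Random loss.** Power = Φ{[d√n − 1.96√(2p̄(1 − p̄))] / √(p1(1 − p1) + p2(1 − p2))}, with p1 and p2 the late rates, p̄ their mean and d their difference.

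- Full data: d√n = 0.01755 × √1064 = 0.5725, so (0.5725 − 0.6025) / 0.3072 = −0.098 and power is 46%.
- Complete cases, 15% lost: n = 0.85 × 1064 = 904, power 40.4%. Simulation gave 40.7%.
- Using 24-hour status: only the unexplained variance is inflated by the loss. Summed over arms, explained is 0.04463 and unexplained 0.04973. Relative information is 0.09435 / (0.04463 + 0.04973/0.85) = 0.915, so the effective n is 973 and power is 42.9%. Simulation gave 43.4%.
- At 20% loss the same sums give 38.4% for complete cases and 41.7% with 24-hour status, recovering about 42% of the lost information.

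**The case against.** The best reply is that the comparison of arms is hardly touched. The plan frames its effect as a relative reduction, and the risk ratio stays between 0.69 and 0.71 in every scenario above, with no inflation of type I error when return depends only on 24-hour status. The power gain is two to three points at 15% loss, on an endpoint that remains underpowered. All of this stands.

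Four stronger readings are tempting, and the documents do not support them.

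- *The 24-hour scan nearly fixes every patient's 30-day result.* It does so only for patent arteries. With half of occlusions reopening, it leaves open the very group that supplies most or all late events.
- *The plan says it will analyse only those who return.* It does not. That is the default of the named tests when no rule is given.
- *Complete cases will overstate the benefit.* That needs occluded patients to return more often. The documents give no loss rate or pattern, and the Background describes RAO as mostly asymptomatic, with 0.2% needing attention for symptoms, so an occluded patient may have no felt reason to return. The bias can go either way.
- *Bias and power loss add up.* The power figures assume random loss, under which there is no bias. With selective return of 95% and 80%, complete-case power is 43%, because most late events are still seen.

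Imputation also has a technical weakness. With almost no late occlusion among patent arteries, an ordinary logistic imputation model is close to separation, and centre terms make it worse with about 62 + 44 = 106 expected late events (1064 × 5.85% and 1064 × 4.095%).

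**Conclusion.** The point holds as a modest, conditional one. The plan leaves the 30-day analysis set and missed scans undefined, its no-loss argument reaches only the 24-hour endpoint, and its named tests discard a predictor worth roughly half of the late-outcome variance.

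If return is linked to 24-hour status, the late rates and the absolute difference are biased: 1.25 to 2.27 points in the scenarios shown, against 1.76. If loss is random, there is no bias, and the avoidable part of the power loss at 15% missing is about 2 to 3 points. The relative effect and the validity of the test are essentially unaffected in both cases.

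These sizes rest on the plan's 11.7%, 30% and 50%, on no new occlusion after 24 hours, and on return rates that are assumptions. This is an inexpensive improvement to a secondary analysis, not a threat to the primary conclusion.

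**What to change.** Add a short paragraph to Statistical analysis that does the following.

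- Define the late RAO analysis as covering all randomised patients.
- Estimate late RAO by standardising over 24-hour Doppler status within arm, as in Step 4, with a standard error that allows for the missing scans. Multiple imputation within arm by 24-hour status is an alternative, provided the method copes with near-zero late occlusion in patent arteries and does not carry many centre terms.
- Do not carry the 24-hour result forward. About half of occlusions reopen, so this would count many reopened arteries as occluded.
- Report complete cases and a worst-case check as sensitivity analyses, with the number scanned at 30 days by arm and 24-hour status.
- State how a missing 24-hour scan is handled, since the method relies on having one.

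The cost is a little more analysis work; no new visits or data are needed. The method relies on scans being missing at random given arm and 24-hour status. That is a weaker assumption than complete cases need for unbiased rates, but it cannot be verified, which is why the worst-case check is needed.
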